Cerebellar tDCS, gait and balance training in PwMS

PI: [name]
IRB ID #: 201912430

Project Details

I. Project Introduction

I.1 *Project to be reviewed by:*
IRB-01

I.2 *Project Title:*
The effects of 4 mA cerebellar transcranial direct current stimulation combined with gait and balance training in people with multiple sclerosis

I.3 *Short Title (optional):*
Cerebellar tDCS, gait and balance training in PwMS

I.4 *Provide a short summary of the purpose and procedures of the study proposed in this IRB application.*

- **DO NOT include information on studies not proposed in this application.**
- **Use LAY terminology only. This must be easily understandable by IRB community members and nonscientists.**
- **DO NOT cut and paste technical abstracts from funding applications that may not be understood by a general audience.**

The purpose of this study is to investigate the effects of cerebellar transcranial direct current stimulation (tDCS) combined with gait or balance training on glucose uptake in the leg muscles as well as gait and balance performance. We will conduct tDCS or SHAM followed by balance or gait training over 9 days. We will evaluate gait and balance with well-established functional tasks and changes in glucose uptake with PET-FDG imaging.

I.5 *Specify your research question(s), study aims or hypotheses (do not indicate "see protocol")*
Our research question is whether tDCS combined with gait and balance training can improve gait and balance performance as well as increase glucose uptake symmetry in the leg muscles of people with multiple sclerosis. We hypothesize that gait, balance, and glucose uptake symmetry will improve in both groups that received training (gait or balance) combined with tDCS compared to the groups that only receive training (sham tDCS). Moreover, we hypothesize that the greatest improvements will be seen in the gait and tDCS group.

I.6 *Background and significance and/or Preliminary studies related to this project. (do not indicate "see protocol")*

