All imaging data will be transferred to the Integrative Neurophysiology Lab in the Department of Health and Human Physiology for analysis. The prior and post-treatment FDG images will be co-registered to the anatomical CT images. Anatomically based volumes-of-interest (VOIs) will be generated manually using the View tool of PMOD. In the upper leg, the knee extensors (rectus femoris, vastus medialis, vastus intermedius, and vastus lateralis) and knee flexors (long and short head of the biceps femoris, semimembranosus, semitendinosus, sartorius, and gracilis) will be identified. In the lower leg, the plantar flexors (gastrocnemius, soleus, peroneus longus, peroneus brevis, flexor digitorum longus, flexor hallucis longus, and tibialis posterior) and the dorsiflexors (tibialis anterior, extensor digitorum longus, and extensor hallucis longus) will be identified. Standardized uptake values (SUV) based on the injected dose and body weight will be calculated for each muscle. Although the participants will fast for a minimum of 6 hours to minimize the impact of endogenous glucose and insulin, SUVs may be affected by blood glucose and insulin levels. Therefore, the SUV data will be analyzed without normalization and, separately, as values normalized to standard blood glucose (adjusted to 100 mg/dL) and/or by using the liver as a reference tissue to allow for comparison across experimental sessions. The data will be analyzed using PMOD Version 4.001 (PMD Technologies LLC, Zürich, Switzerland). Asymmetry indices (AIs) will be calculated to determine the magnitude of asymmetry in SUVs between the legs using a previously used equation^{23,82}. An AI greater than 10% will be considered asymmetric. Spearman's correlation will be used to test whether the change in FDG uptake is significantly related to the change in walking and balance scores after ctDCS and training. We will use a liberal significance threshold to avoid type II errors because the relatively low number of subjects in this study leads to conservative testing. The level of statistical significance for all brain imaging analyses is $p < 0.005$ without correction.

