A stimulation (sham vs. 4 mA) by training (balance vs. gait) by time (24 hours, 2 weeks, and 4 weeks) ANCOVA with baseline measurements as covariates will be conducted on each outcome variable (e.g., distance walked on the 6MWT and FGA score) to compare the short- and long-term effects of gait and balance training combined with ctDCS. Levene's test and normality tests (QQ plots, Shapiro Wilk test, and histograms) will be used to test the statistical assumptions. Post-hoc testing (paired and unpaired t-tests) and effect sizes (Cohen's d) will be calculated to clarify significant main or interaction effects. Significance will be accepted at $p < 0.05$ and adjusted with a Bonferroni correction. Statistical analyses will be performed using SPSS 27 (IBM Corp, Armonk, NY, USA).

XI.2*Provide the rationale or power analysis to support the number of subjects proposed to complete this study.*

We used effect sizes (Cohen's $d = 2.08$ and 1.37 , respectively) from Pilloni et al. 202060 and Hebert et al. 201146 to calculate the required sample size. With a significance fixed at $p = 0.05$ and 80% power, we will require 40 total subjects ($n = 10$ in each group) to properly power the hypothesis test for a statistically significant change. Based on this calculation and the assumption of a standard drop out rate of approximately 20%, we propose to recruit 48 total subjects ($n = 12$ in each group).

XII. Future Research

XII.1 *Do you wish to keep any information about subjects involved with this research project so that members of the current research team may contact them in the future for your own research projects?*
Yes

XII.2 *Do you wish to keep any information about subjects involved with this research project so that other researchers may contact them for future research?*
Yes

XII.3 *List the data or information you will keep:*
Contact information and outcome of the phone questionnaire.

XII.4 *Does this project involve storing any data, tissues or specimens for future research?*
Yes – contribution for future use is mandatory for participation in the study

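### Follow-up t-tests after the baseline-adjusted ANCOVA carry no covariate and lose precision; separately, the 24-hour v 2- and 4-week time effect should not be read as retention

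*Combined protocol and SAP*

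**What the plan says.** **Model.** Section XI.1 describes a stimulation by training by time "ANCOVA with baseline measurements as covariates will be conducted on each outcome variable". The time factor has three levels: 24 hours, 2 weeks and 4 weeks.

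**Follow-up tests.** The same paragraph continues: "Post-hoc testing (paired and unpaired t-tests) and effect sizes (Cohen's d) will be calculated to clarify significant main or interaction effects". Significance is set at 0.05, "adjusted with a Bonferroni correction", with no count of comparisons. Nothing ties the t-tests or Cohen's d to adjusted means or to the model's error term. Change is mentioned elsewhere: section XI.2 sizes the trial "to properly power the hypothesis test for a statistically significant change", and the imaging paragraph of XI.1 correlates FDG uptake with "the change in walking and balance scores after ctDCS and training". Raw and change scores are therefore both possible readings.

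**Hypotheses.** Section I.5 expects tDCS to beat sham within each type of training, and that "the greatest improvements will be seen in the gait and tDCS group".

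**Test conditions.** In section VII.E.6, Session 2 (baseline) lists a 20-minute treadmill walk and PET scan before the gait and balance tests. Session 12 (24 hours) repeats that battery. FDG requires a fast of at least 6 hours. Sessions 13 and 14 (2 and 4 weeks) list only the fatigue questionnaire and the functional tests. Sessions 2 and 12 last about three hours, Sessions 13 and 14 about one.

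**The concern.** The authors chose to adjust for baseline, and then specify follow-up tests that, as written, do not use it. A pairwise claim would rest on a noisier comparison than the fitted model can supply and could disagree with that model. With about 10 patients per group and a Bonferroni correction, lost precision matters.

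The comparisons most exposed are the 10 v 10 simple effects: active v sham within one training, and gait plus tDCS against each other group. The section I.5 claims about each training, and about which group does best, need these. The omnibus stimulation effect does not.

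The time factor raises a separate, secondary question. A change between 24 hours and weeks 2 to 4 could be read as benefit lasting or fading, when the conditions before testing also changed.

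**Working it through.** **Inputs.** From section XI.2: d = 1.37 (the smaller of two planning effects), alpha 0.05, 80% power, 10 per group. Assumed: r = 0.5 / 0.7 / 0.8, two-sided tests, and d = 1.37 read as an ordinary between-group effect.

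**The plan's own figure.** A two-sided t-test at 10 v 10 has noncentrality 1.37 × √(10/2) = 3.06 on 18 df, giving 82.6% power; 9 v 9 gives 77.9%. So 10 per group and 40 in total are reproduced, at an uncorrected 0.05.

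**Variance.** With SD 1 at both visits, the per-patient variance is 1 for raw scores, 2(1 − r) for change scores and 1 − r² after adjustment.
- Raw ÷ adjusted = 1/(1 − r²): 1/0.75 = 1.33; 1/0.51 = 1.96; 1/0.36 = 2.78.
- Change ÷ adjusted = 2(1 − r)/(1 − r²) = 2/(1 + r): 2/1.5 = 1.33; 2/1.7 = 1.18; 2/1.8 = 1.11.

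These ratios need r only, not d.

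**Illustrative power at one visit, d = 1.37, 10 per group.** Effective d is 1.37 (raw), 1.37/√(2(1 − r)) (change) and 1.37/√(1 − r²) (adjusted). The t-tests have 18 df. The contrast from a four-group ANCOVA has 40 − 4 − 1 = 35 df.

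| Bonferroni count | Raw t | Change t (r = 0.5 / 0.7 / 0.8) | Four-group adjusted contrast (r = 0.5 / 0.7 / 0.8) |
|---|---|---|---|
| 4 | 62% | 62 / 87 / 97% | 81 / 94.5 / 99% |
| 12 | 44% | 44 / 74 / 92% | 68 / 88 / 97% |

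An adjusted test fitted to two groups only (17 df) gives 76 / 92 / 98% and 60 / 82 / 95%. Those are not the power of the four-group contrast. The formula ignores chance baseline imbalance, which lowers adjusted power slightly.

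**Disagreement with the model.** Trials were simulated with four groups of 10, one visit, and a tDCS effect of 1.37 SD in both trainings.
- 10 v 10 simple effect, tested whatever term is significant, alpha 0.05: the raw t-test reaches a different verdict from the four-group contrast in about 12 / 16 / 17% of trials, the change t-test in about 12 / 3 / 0.4%. Part of this comes from pooled error and df: a two-group adjusted test also differs, in about 4 / 1 / 0.3%.
- 20 v 20 follow-up of the stimulation main effect, raw scores: about 1% at alpha 0.05, and 5–7% at 0.05/6 (six being all pairs of four groups).
- In this scenario the stimulation-by-training interaction is significant in only about 5% of trials.

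**Type I error.** With no true effect, the raw, change and adjusted tests all reject in 4.9–5.2% of trials. In the roughly 32% of trials where chance baseline imbalance exceeds one standard error, the raw t-test rejects in about 9 / 12 / 14%, while the adjusted test stays near 5%.

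**Time effect.** Suppose test conditions shift scores by s at one visit. For two arms at that visit, (A + s) − (B + s) = A − B, so a common shift cancels from same-visit contrasts and from interactions with time. It remains in the 24-hour v 2- and 4-week main effect and in within-arm paired changes across those visits. The documents give no value for s.

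**The case against.** The strongest reply is that the follow-up tests are conditional: XI.1 runs them to explain a significant term. If tDCS works equally in both trainings, the significant term is usually the stimulation main effect. Its follow-up is 20 v 20, where disagreement is about 1% at alpha 0.05. This stands. A reader might infer that 12–17% of trials would reach a different conclusion. That rate applies only if simple effects are tested whatever term is significant, which XI.1 does not say.

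It also stands that tDCS benefit as such is tested first by baseline-adjusted terms using all patients, and that change scores with a high r leave little loss. Paired comparisons between follow-up visits already use each patient as their own control, so the missing covariate costs little there.

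The reply does not remove the point. The claims for each training and for the best group need pairwise comparisons, and the text describes these without adjustment.

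On the time effect, one can fairly say that the section I.5 hypotheses are between groups, that the ANCOVA time factor excludes baseline, and that the documents do not say whether patients are still fasting at the functional tests. All of that is right, and it confines the point to how the time effect is interpreted. The listed order is nonetheless the natural reading, because the form asks for procedures in sequence.

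**Conclusion.** The point holds as a loss of precision in the follow-up comparisons, with possible disagreement with the fitted model. At assumed r = 0.5 / 0.7 / 0.8 the variance penalty is 1.33 / 1.96 / 2.78 times for raw scores and 1.33 / 1.18 / 1.11 times for change scores. The power figures are illustrations only: they also require d = 1.37 to be a between-group effect on the contrast in question, which the documents do not establish, least of all for gait plus tDCS against balance plus tDCS.

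Three stronger readings are not supported. The t-tests do not inflate type I error overall. The trial's main effects and interactions are not unadjusted. And the differing test conditions do not bias the between-arm comparisons at 2 and 4 weeks if the shift is common to all arms. The time point stands only as a limit on reading the time main effect, or within-arm changes across those visits, as retention or fading. Its size and direction are unknown.

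**What to change.** In section XI.1, replace the post-hoc t-tests and raw Cohen's d with Bonferroni-adjusted contrasts of baseline-adjusted marginal means from the fitted ANCOVA, with effect sizes based on those adjusted differences. Name four contrasts:
1. active v sham within gait training;
2. active v sham within balance training;
3. gait plus tDCS v balance plus tDCS;
4. gait plus tDCS v sham plus balance.

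Contrasts 1, 3 and 4 together set gait plus tDCS against every other group. State whether the correction covers one visit (four contrasts) or all three (4 × 3 = 12). If power is quoted, use the four-group values and state the assumed r and d; do not quote the two-group figures.

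Add that 2- and 4-week claims rest on same-visit between-arm contrasts or on interactions with time, and that the time main effect and within-arm paired changes from Session 2 or 12 to Sessions 13 and 14 will not be read as retention or fading.

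The cost is wording only: same model, software, data, visits and patients. Correcting for twelve contrasts rather than four costs power (81 to 68% at r = 0.5 in the illustration), which is why the count should be fixed beforehand.

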STRENGTH TESTING: Strength testing will be performed in a sitting position on an isokinetic dynamometer (CSMi, Stoughton, MA, USA). The subject will be secured with Velcro bands to help isolate the knee joint and the range of motion will be set between 100° and 0° of flexion. Strength testing will begin with a 15-repetition warm up of the knee extensors and flexors at 60/s (concentric/concentric). After a 30 second rest, 3 sets of 1 maximal effort isometric contraction of the knee extensors and flexors will be performed at 65° and 30°, respectively, with 30 s of rest between each set. Isokinetic strength testing will consist of 3 sets of 1 maximal effort knee extension and flexion (60/s, concentric/concentric) with 30 s of rest between each set. All testing will be completed on both legs and the largest torque obtained from a given muscle group in any of the strength testing conditions (isometric or isokinetic) will be used to verify leg dominance.

FUNCTIONAL GAIT ASSESSMENT (FGA): The FGA is a valid measure of walking balance and consists of 10 challenging tasks, such as walking with a narrow base of support (i.e., tandem stance), walking backwards, and walking with eyes closed. Each item is graded from 0 (severe impairment) to 3 (normal performance), with a maximum score of 3068. The minimal clinical important difference (MCID) for the FGA has not been established in PwMS. However, in other neurological populations, a MCID of 4-6 points has been suggested.

TIMED 25-FOOT WALK TEST (T25FW): The T25FW test resembles relevant daily life situations, such as walking across a signaled intersection, is well-established and has very good psychometric properties. In a cordoned-off hallway, subjects will be instructed to walk as fast as possible between two points separated by 25 feet during two separate trials65. The shortest time it takes to complete the 25-foot walk will be the main outcome variable. Gait characteristics will also be recorded using six inertial sensors (OPAL inertial motion units [APDM, Portland, OR, USA]) located on the chest/sternum, each wrist and foot, and on the lower back (5th lumbar). A 20% decrease in the time it takes to complete the T25FW has been established as a significant change in PwMS.

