BERG BALANCE SCALE (BBS): The BBS is a valid and reliable assessment of balance during static (e.g., standing with eyes closed) and dynamic (e.g., completing a 360-degree turn) conditions. A cut-off score of 44 has been established as a criterion to identify PwMS with a high fall risk. Furthermore, it has been shown that the minimal clinically important difference (MCID) for the BBS in PwMS is 3 points.

STATIC POSTUROGRAPHY: Static posturography will be examined on a Balance Plate (Balance Tracking Systems, San Diego, CA, USA). Participants will stand on both firm (i.e., the force plate) and compliant (i.e., a 6 cm Airex Balance Pad Elite 76 [Airex AG, Sins, Switzerland] placed on the force plate) surfaces with their eyes open and with their eyes closed for one minute each. The addition of a foam pad increases the difficulty of maintaining balance by changing foot pressure distribution and decreases the input of cutaneous mechanoreceptors and joint receptors. The center of pressure average movement velocity in the anterior-posterior and medial-lateral directions and the area of an ellipse that encapsulates 95% of the 2D area explored will be the primary outcomes.

6-MINUTE WALK TEST (6MWT): The 6MWT is considered the “gold standard” for a long walking test in interventional research. The subjects will be led to a cordoned-off hallway to perform the walk. Subjects will be instructed to walk as far as possible between two points separated by 30 m for 6 min. Gait characteristics and distance walked will be calculated and recorded using six inertial sensors (OPAL inertial motion units [APDM, Portland, OR, USA]) located on the chest/sternum, each wrist and foot, and on the lower back (5th lumbar).

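### Effect sizes are planned only as follow-up to significant ANCOVA effects, with no confidence intervals, so small or moderate effects will be overstated on average and non-significant outcomes have no planned estimate

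*Combined protocol and SAP*

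**What the plan says.** Section XI.1 sets out a stimulation by training by time model with three post-treatment visits: an "ANCOVA with baseline measurements as covariates will be conducted on each outcome variable". Post-hoc t-tests and Cohen's d then follow; they "will be calculated to clarify significant main or interaction effects". On the error rate it says "Significance will be accepted at $p < 0.05$ and adjusted with a Bonferroni correction", without giving the number of comparisons. No confidence interval is mentioned, and no other effect estimate is planned for the ANCOVA outcomes. The same section separately plans asymmetry indices and Spearman correlations for the imaging data; neither depends on a significant ANCOVA effect.

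Section XI.2 sets 10 per group (40 in total) and recruits 12 per group (48). In the 2 x 2 layout a stimulation main effect therefore compares 20 to 24 with 20 to 24.

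Section VII.E.6 quotes reference values that XI.1 never uses. For the Berg Balance Scale, the "minimal clinically important difference (MCID) for the BBS in PwMS is 3 points". For the timed walk, "A 20% decrease in the time it takes to complete the T25FW has been established as a significant change in PwMS". For the Functional Gait Assessment, "a MCID of 4-6 points has been suggested", but in other neurological populations; the same paragraph says that no value is established in MS.

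**The concern.** An estimate that appears only after its test has passed is drawn from the upper part of its sampling distribution. The smaller the true effect relative to its standard error, the larger the average overstatement. With 10 to 12 per cell that matters unless effects are large.

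The outcomes that fail the test are the other half of the problem. With no estimate and no interval, a reader cannot separate a tDCS effect too small to be useful from a trial too small to see it. Cohen's d is also in SD units, so even where it is reported it does not say how many Berg points or what change in walking time was gained.

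At stake is how large the tDCS effect on gait and balance is, which is what anyone planning a later trial would take from this one.

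**Working it through.** **1. The plan's own figure.** With d = 1.37, two-sided alpha 0.05 (sidedness is not stated) and a two-sample t-test, 10 per group gives 82.6% power and 9 gives 77.9%. So 4 x 10 = 40, and 40 x 1.2 = 48. This reproduces XI.2 and fixes the cell size used below.

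**2. Outer bound: one visit, no baseline adjustment.** The smallest significant |d| is t(0.975; 2n - 2) x sqrt(2/n).
- 10 v 10: 2.101 x sqrt(0.2) = 0.94.
- 20 v 20: 2.024 x sqrt(0.1) = 0.64.

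At a true d of 0.5, simulation (400,000 draws per setting) gives a mean significant |d| of 1.24 for 10 v 10 (1.24/0.5 = 2.5 times) and 0.87 for 20 v 20 (1.7 times). This is not the planned analysis. It ignores the baseline covariate and the three visits, and the plan's condition is a significant ANCOVA effect, not a significant two-arm t-test.

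**3. The planned condition: stimulation main effect in the baseline-adjusted three-visit model.** The documents give no correlations, so these are assumptions: baseline with post-treatment (rb) 0.5, 0.7, 0.8, paired with between-visit (rv) 0.7, 0.8, 0.85. The effect is taken as constant over visits and trainings, with 20 per stimulation level.
- Residual variance of the three-visit mean, in SD squared: V = (1 + 2rv)/3 - rb².
- Standard error: SE = sqrt(2V/20).
- Signal: L = d/SE.
- Critical value: c = 2.03 (40 subjects less 5 parameters = 35 df).
- Probability of passing: P = Φ(L - c).
- Average inflation of the reported adjusted difference: 1 + φ(L - c)/(L x P). The opposite tail is negligible.

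| rb, rv | V | SE | d = 0.3: P, inflation | d = 0.5: P, inflation | d = 0.8: P, inflation |
|---|---|---|---|---|---|
| 0.5, 0.7 | 0.550 | 0.235 | 0.23, 2.0 | 0.54, 1.34 | 0.92, 1.05 |
| 0.7, 0.8 | 0.377 | 0.194 | 0.31, 1.7 | 0.71, 1.19 | 0.98, 1.01 |
| 0.8, 0.85 | 0.260 | 0.161 | 0.43, 1.5 | 0.86, 1.08 | 1.00, 1.00 |

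Example, first row at d = 0.5: L = 0.5/0.2345 = 2.13; P = Φ(0.10) = 0.54; inflation = 1 + 0.397/(2.13 x 0.54) = 1.34. Simulating the same model gives passing rates of 54%, 70% and 84% at d = 0.5. Expressed as Cohen's d, the inflation is 1.37, 1.23 and 1.12, slightly higher because d has a small upward bias of its own in small samples.

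**4. Bonferroni.** The number of comparisons is unstated. With an assumed factor of 6, c is about 2.8 and the same formula gives about 1.6, 1.4 and 1.2 at d = 0.5, and about 2.5, 2.1 and 1.8 at d = 0.3.

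**5. What goes unreported.** From the table, the stimulation effect fails the test in 57% to 77% of trials at d = 0.3 and in about 14% to 46% at d = 0.5. An observed single-visit d of 0.5, not significant, has a 95% interval of -0.13 to 1.13 at 20 v 20 and -0.40 to 1.38 at 10 v 10. Those intervals show that the data would exclude neither no effect nor a large one; a p-value alone does not.

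**The case against.** The best defence has four parts.

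- **The text does not say only.** The sentence describes post-hoc follow-up in an IRB form, and nothing says that group means will be withheld. That is true. But it is the one place where an effect size is planned for these outcomes, and nothing commits the trial to an estimate or interval for the rest.
- **The condition is easier to pass than a two-arm t-test.** This stands. Any significant main or interaction effect opens the follow-up, and a cell-level d below 0.94 can then be reported. The 2.5-fold figure is therefore an outer bound, not the expected size. It is not irrelevant, however: the hypothesis in I.5 that gait training with tDCS does best rests on cells of 10 to 12.
- **Under the plan's own assumptions the bias is small.** This also stands. Even with the single-visit t-test at 10 v 10, a true d of 1.37 is inflated by about 16%, and 38% of significant estimates fall below the truth; at 2.08 the inflation is negligible. A reader might infer that every reported effect is too high, or that most outcomes will have no estimate. The bias is in the average, and how many outcomes miss significance depends on true effects that the documents do not give. The imaging asymmetry indices and correlations lie outside the condition altogether.
- **Comparison with minimal important differences is partly a matter of preference.** Accepted. Such thresholds may describe change within a person, and the FGA value is not established in MS, so they can serve only as context.

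It is also tempting to read the large planning values in XI.2 as this harm already at work. XI.2 says only that they come from two cited studies; nothing in the documents shows how those estimates were selected.

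**Conclusion.** The point holds in a limited form. Cohen's d is tied to significant ANCOVA effects, no interval is specified, and non-significant outcomes have no planned estimate. The upward bias is an average one and depends on the true effect. For the stimulation main effect it is about 1.5 to 2.0 times at d = 0.3, 1.1 to 1.3 times at 0.5 and negligible at 0.8.

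These figures assume 10 per cell, two-sided alpha 0.05, an effect constant over visits and trainings, and the correlations listed, none of which the documents supply. With all 48 analysed the bias would be somewhat smaller. A Bonferroni adjustment, a short-lived effect, or an effect confined to one training would make it larger.

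The missing estimates and intervals do not depend on any of these assumptions. The change should be made: it is a reporting weakness that is cheap to remove, and it does not invalidate the planned tests.

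**What to change.** In XI.1, replace the sentence on post-hoc effect sizes with: *For every functional outcome and visit, whatever the p-value, report the baseline-adjusted tDCS minus sham difference in native units with its 95% confidence interval, overall and within each training, with Cohen's d alongside for all outcomes.*

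Post-hoc tests can still follow significant effects. The Berg 3-point and timed-walk 20% figures may be shown beside the results for context. The FGA 4 to 6 points should appear only with the caveat that it comes from other neurological populations.

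The cost is a longer results table. The estimates and intervals come from the models already planned; no new data, visits or participants are needed.

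### Holm's step-down procedure could replace single-step Bonferroni for the post-hoc t-tests at no cost in error control; the gain in power is modest

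*Combined protocol and SAP*

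**What the plan says.** Section XI.1 specifies, for every outcome, "A stimulation (sham vs. 4 mA) by training (balance vs. gait) by time (24 hours, 2 weeks, and 4 weeks) ANCOVA" adjusted for baseline; the analysis "will be conducted on each outcome variable (e.g., distance walked on the 6MWT and FGA score"). Follow-up testing is described as "Post-hoc testing (paired and unpaired t-tests) and effect sizes (Cohen's d"), which "will be calculated to clarify significant main or interaction effects". The next sentence sets the error rule: "Significance will be accepted at $p < 0.05$ and adjusted with a Bonferroni correction".

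On the natural reading, the t-tests open only after a significant omnibus effect and are then corrected by single-step Bonferroni. The section does not say which tests form the family being corrected, and it mentions no step-down method.

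Section XI.2 sizes the trial without that correction: "With a significance fixed at $p = 0.05$ and 80% power", from "effect sizes (Cohen's $d = 2.08$ and 1.37 , respectively"), leading to the statement that "we will require 40 total subjects ($n = 10$ in each group").

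**The concern.** With 10 evaluable participants per arm, power lost without a matching gain in error control is worth recovering. Single-step Bonferroni tests every member of a family of m at 0.05/m, even after some members have been rejected. Holm relaxes the threshold after each rejection and needs no extra assumption about how the tests are correlated. The plan aims to describe both short- and long-term effects, so more than one rejection within an outcome may be wanted, and second and later rejections are where the two methods differ.

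**Working it through.** **1. The plan's own figure.** Inputs from XI.2: d = 1.37 and 2.08, alpha 0.05 (two-sided assumed, since sidedness is not stated), power 80%. A two-sample t-test with d = 1.37 needs n = 9.43, so 10 per group and 4 × 10 = 40 in total. This reproduces the plan. With d = 2.08 only 5 per group are needed, so d = 1.37 drives the size.

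**2. The two rules.** Order the p-values p(1) ≤ … ≤ p(m).

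- Bonferroni rejects each p(i) ≤ 0.05/m.
- Holm starts at the smallest and continues while p(i) ≤ 0.05/(m − i + 1).

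For m = 3 the Holm thresholds are 0.0167, 0.025 and 0.05, against 0.0167 throughout for Bonferroni. No Holm threshold is below 0.05/m, so Holm rejects all that Bonferroni rejects. The first thresholds are equal, so the chance of at least one rejection is identical. This holds for any family, so it does not depend on the family that XI.1 leaves open.

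**3. What Holm cannot change.** Power of one two-sample t-test at d = 1.37 and n = 10 per arm:

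| Alpha | Power |
|---|---|
| 0.05 | 82.6% |
| 0.05/3 | 66.4% |
| 0.05/6 | 55.2% |

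The sample size rests on the first row. The first step of Holm, like Bonferroni, works at the second or third.

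**4. 4 mA versus sham at each of three visits, behind the stimulation-by-time gate.** Simulated with 10 per arm. Visit correlation (rho) is not in the documents and is assumed. The gate is a multivariate interaction test. Average power per true contrast:

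| True d at the three visits | rho | Bonferroni | Holm | Gain (points) |
|---|---|---|---|---|
| 1.37, 0, 0 | 0.5 | 61.0% | 61.1% | 0.1 |
| 1.37, 0, 0 | 0.85 | 66.6% | 66.6% | 0.0 |
| 1.37, 0.7, 0 | 0.5 | 32.5% | 34.2% | 1.7 |
| 1.37, 0.7, 0 | 0.85 | 41.7% | 44.0% | 2.3 |
| 1.37, 1.37, 0 | 0.5 | 57.3% | 60.4% | 3.1 |
| 1.37, 1.37, 0 | 0.85 | 66.4% | 69.8% | 3.4 |

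For 1.37, 1.37, 0 behind an F gate, power to show both true effects is 49.9% versus 56.7% (rho 0.6) and 56.5% versus 63.2% (rho 0.8), a gain of about 7 points. With an effect at one visit only, the gain is essentially nil.

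The gain is larger if effects exist at all three visits but differ enough to open the gate. For 2.08, 1.37, 0.7 (illustrative), average power is 50.7% versus 56.2% (rho 0.6) and 59.6% versus 66.4% (rho 0.8). Power for all three is 11.2% versus 22.2% and 16.7% versus 30.9%.

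**5. Six pairs among four arms of 10, behind the omnibus gate.**

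| Pattern | Measure | Bonferroni | Holm |
|---|---|---|---|
| Two arms higher by 1.37 | Average per true pair | 60.8% | 66.1% |
| | All four true pairs | 28.5% | 39.7% |
| | At least one | 88.9% | 88.9% |
| | Family-wise error | 0.017 | 0.030 |
| One arm higher by 1.37 | Average per true pair | 60.9% | 64.1% |
| | All true pairs | 37.6% | 44.2% |

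**6. Can the omnibus test replace the correction?** With three visit means, once the overall null is false at most one of the three pairwise nulls can still be true. A valid time test followed by unadjusted pairwise tests then controls the error by closed testing. With N = 40, one visit shifted by 0.4 SD and rho 0.6 (assumed), average power is 62.6% (Bonferroni), 66.2% (Holm) and 74.7% (gate alone).

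Family-wise error of the gate-alone rule:

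- Three visit pairs, F gate, sphericity holding: 0.047 to 0.050.
- Three visit pairs, uncorrected F gate, sphericity failing (epsilon about 0.6 to 0.8): 0.055 to 0.065. A Greenhouse-Geisser gate brings this back to about 0.05 or below.
- 4 mA versus sham at each visit, effect at one visit only: about 0.074 to 0.081 at d = 1.37 and 0.079 to 0.095 at d = 3. A true interaction can leave two visit nulls true, each tested at 0.05.
- Six arm pairs: 0.095 to 0.118.

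**The case against.** The strongest reply is that nothing here is wrong. Bonferroni is valid and pre-specified, gives simple simultaneous intervals, and is not severely conservative: its family-wise error for six contrasts (4 mA versus sham in two training types at three visits), without the gate, is about 3.6 to 4.8%. That Holm is never less powerful is a textbook fact, not a defect peculiar to this trial. The larger power problem is that 10 per arm was computed at unadjusted 0.05, which Holm leaves untouched. All of this stands and is why the point ranks as minor. It does not remove the case for a costless improvement in small arms.

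A reader might infer a much larger benefit by putting d = 1.37 at all three visits and ignoring the gate. The chance of showing the effect at every visit then appears to rise from 41–53% to 62–69%. The documents do not support that reading. XI.1 opens post-hoc tests only after a significant effect, and with equal effects at every visit there is no stimulation-by-time interaction, so that gate opens in only about 5% of runs. What would normally open is the stimulation main effect, which has two levels and needs no post-hoc family.

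**Conclusion.** The point holds as a minor refinement. For whatever family is meant, Holm gives the same family-wise error control as the planned Bonferroni step and equal or greater power. With 10 per arm and d = 1.37 at one or two visits, the gain behind the interaction gate is 0 to about 3 points of average power per true contrast and 0 to 7 points for all true effects. For the four-arm pairs it is about 3 to 5 and 7 to 11 points. It can be larger if unequal effects exist at all three visits. These sizes rest on assumed visit correlations and effect patterns, and on reading XI.1 as Bonferroni applied after an omnibus test. The ordering of the two methods rests on none of these.

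A reader might also infer that the gate makes any correction unnecessary wherever three visits are involved. That is too strong. It is true only for visit-versus-visit comparisons, only if the family is those three contrasts, and only with a time test robust to non-sphericity; XI.1 lists Levene's test and normality checks but no sphericity check. It fails for 4 mA versus sham at each visit and for the arm pairs, the comparisons closest to the hypothesis in section I.5. If the correction is meant to span outcomes or ANCOVA effects, the gate cannot replace it, whereas Holm still can.

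**What to change.** In XI.1, replace the Bonferroni clause with: *adjusted by Holm's step-down procedure within each family*. The sentence presupposes that each family is named, so state which contrasts it contains.

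Optional and narrower: if a family consists only of the three pairwise visit comparisons, allow unadjusted tests after a significant omnibus time test that is Greenhouse-Geisser-corrected or multivariate. State that this does not extend to 4 mA versus sham at each visit or to the four-arm pairs, where Holm applies.

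The cost is one or two sentences and ordering p-values by hand or in a spreadsheet, with no extra participants or data. The one drawback is that simultaneous confidence intervals matching Holm are less simple than Bonferroni intervals. The change should not be presented as restoring the 80% power claimed in XI.2.
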